11.3.2 Form

Dexamethasone is a white to practically white, odorless, crystalline powder. It is available in 4 mg tablets for oral administration. Each tablet contains dexamethasone as the active ingredient, and the following inactive ingredients: calcium phosphate, lactose, magnesium stearate, and starch. The tablet shell may contain the following: D&C Yellow 10, FD&C Yellow 6, and/or FD&C Blue 1.

11.3.3 Storage and Stability

At the study site, all study drugs will be stored in a locked, safe area to prevent unauthorized access.

Dexamethasone should be stored at controlled room temperature, 68-77°F (20-25°C) and not frozen, and according to label requirements.

11.3.4 Handling

Dexamethasone should be handled by trained pharmacy staff. The use of gloves and other appropriate protective clothing is recommended as necessary.

11.3.5 Availability

Dexamethasone supply will be obtained through commercial supply.

11.3.6 Preparation

Dexamethasone is an oral drug and does not require specific preparation details.

11.3.7 Ordering

The investigator or designee will order drug supply from commercial supply.

11.3.8 Accountability

The investigator is responsible for keeping accurate records of the clinical supplies received from AFT or designee, the amount dispensed to patients and the amount remaining at the conclusion of the study.

11.3.62 Destruction and

Sites may destroy unused study drug according to their institutional policies. If any study drug is lost or damaged, its disposition should be documented in the source documents. Patients will be instructed to return empty containers (if applicable) and unused investigational product to the clinic site.

12. Data Collection and Management/ Data and Specimen Submission

12.1. Data Collection and Submission

Data collection for this study will be done through the Medidata® Rave clinical data management system. Access to the study in Rave EDC is granted through the iMedidata application to all persons with the appropriate roles assigned in AFT CTMS System. See Data Entry Guidelines for additional instructions.

12.2. Specimen Collection and Submission

Bone marrow aspirates will be collected at a pre-treatment and end of cycle 1 correlative. Two 2 ml tubes will be collected at each time point.

Peripheral blood will be collected at pretreatment and after cycles 1, 3, and 6 for immunome studies. 15 ml of blood will be collected at each time point.

Table 16 Research Blood and Body Fluid to be Collected

Correlative Study (Section 13 for more information)	Mandatory or Optional	Blood or Body Fluid being Collected	After registration, prior to start of treatment	At completion of Cycle 1, 3, and 6
immunome studies	Mandatory	Peripheral blood	X	X
	Mandatory	Peripheral blood	X	X
bone marrow aspirates	mandatory	Bone marrow fluid	X	X*

*at the end of Cycle 1 only

Details for processing and shipping of specimens can be found in the study specific correlative science manual.

13. Correlative Studies

To be performed in [REDACTED]

13.1. Peripheral Blood and Bone Marrow Samples

Peripheral blood samples and bone marrow samples will be sent to the Alliance Foundation Biorepository, who will process the samples before sending them to City of Hope. Peripheral blood and bone marrow aspirates will be used to analyze Th1/Th2 response in treated patients and the bone marrow aspirates will be used to isolate CD-138+ myeloma cells for the analysis of Btk, microRNA (miR) and mRNA expression for correlation with outcomes.

13.2. Immunome

The immunome correlative will be completed in the expansion phase only. Peripheral blood will be collected at pre-treatment, after cycles 1, 3, and 6, and the PBMC fraction will be used to quantify immune subset changes over the course of treatment including B cells, cytotoxic T cells, T regulatory cells, T central memory cells, NK cells, NKT cells, and B-cell subsets by flow cytometry to assess for any changes that may correlate with outcome. Specifically, 5x106 PBMC will be stained using Maxpar® Direct™ Immune Profiling System and detect by mass cytometry analysis. We are planning to collect at least 40 longitudinal samples for the analysis.

At Pre-treatment and end of cycle 1 (before start of cycle 2) bone marrow aspirates will be collected for total RNA sequencing. Specifically, CD138+ plasma cells will be purified from total marrow cells of patients by Human Whole Blood CD138+ Selection Kit (Cat#18387, Stem Cell Technologies), as described in section 13.3. We are planning to perform RNA sequencing in total 10 longitudinal samples isolated from 5 patients.

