	
there are no other higher dose levels to be tested, this will be considered the MTD.
 
Patients will return to the clinic every 28 days for physical exams, laboratory assessments and review of side effects.
 
Patients who do not have disease progression and have not experienced unacceptable toxicities will be eligible to continue protocol treatment at their current dose level until disease progression, unacceptable toxicity, or refusal. Those patients who have not experienced progression of disease but have unacceptable toxicity may be eligible for re-treatment at a lower dose.
 
Part 2: Dose Expansion Once the MTD has been established or determined, 4-10 additional patients will be treated at the MTD of lenalidomide and ibrutinib at the same schedule as above. Dexamethasone will be given at the same dose as in the dose escalation portion of the study.
 
Patients who have not had disease progression and have experienced acceptable toxicity will be eligible to continue protocol treatment at their current dose level until disease progression, unacceptable toxicity, or refusal. Those patients who have not progressed and who have experienced unacceptable toxicity may be eligible for re-treatment at a lower dose. A maximum of 2 reductions are allowed.
 
Criteria for discontinuation of protocol therapy include:
 
• Tumor progression• Request by the patient to withdraw• Unacceptable adverse events• Treatment delay of >4weeks• Intercurrent illness which would, in the judgment of the investigator, affect assessments of clinical status to a significant degree that require discontinuation of drug• Non-protocol chemotherapy, or an experimental drug during the trial 
Patients who discontinue treatment for any of the above reasons will go to survival follow-up. Once a patient has entered the survival follow-up phase of the trial, his/her therapy is at the discretion of the treating physician. Patients' charts will be reviewed for progression and survival endpoints during visits with treating physicians.
 
Bone marrow aspirate will be collected at pre-treatment and at end of cycle 1 for micro-RNA profiling and gene expression for correlative studies.
 
Peripheral blood will be collected at pre-treatment, after cycles 1, 3, 6 and 12 for immunome correlative studies.

--	---

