14.1. Overview of the Study Design

This is a single-arm, open label, phase Ib study of Ibrutinib in combination with lenalidomide and dexamethasone in adult (age 18 years and older) patients with relapsed/refractory MM. A 3+3 phase I clinical trial design as described in Section 6.0 was chosen to determine the MTD of Ibrutinib in combination with lenalidomide given on days 1-21 of a 28-day cycle and dexamethasone given orally weekly. An expansion cohort of 10 patients will be treated at the MTD to gather additional safety and anti-tumor activity data.

As of April 15, 2021, 2 patients have been enrolled onto dose level 2.

- If none of the first 3 patients treated at dose level 2 develops a DLT, then the next cohort of 3 patients will be enrolled onto dose level 3 and biospecimen collection will begin for all subsequent patients enrolled.
- If one of the 3 patients treated at dose level 2 develops a DLT, then the next cohort of 3 patients will be enrolled at dose level 2 and correlative biospecimens will be collected from these patients.
 - o If 2 or more of the 6 patients treated at dose level 2 develops a DLT then an additional 10 patients will be enrolled onto dose level 1 so that a total of 10 patients will have provided biospecimens at the MTD. (Note: Total sample size will be 6 [from dose level 1] + 6 [from dose level 2] + 10 [for dose expansion] = 22. Biospecimens will be available for 10 patients treated at the MTD.)
- If 2 or more of 3 patients treated at dose level 2 has an DLT, an additional 10 patients will be enrolled onto dose level 1 to further assess safety and collect specimens for correlative aims. (Note: Total sample size will be 6 [from dose level 1] + 3 [from dose level 2] + 10 [for dose expansion] = 19. Biospecimens will be available for 10 patients treated at the MTD.)
- If at most 1 of 6 patients treated at dose level 2 develops a DLT and 2 or more of the 3-6 patients treated at dose level 3 develops a DLT, then an additional 7 patients will be enrolled onto dose level 2 so that a total of 10 patients will have provided biospecimens at the MTD. (Note: Total sample size will be 6 [from dose level 1] + 6 [from dose level 2] + 6 [maximum number anticipated on dose level 3] + 7 [for dose expansion] = 25. Biospecimens will be available for 10 patients treated at the MTD.)

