- If at most 1 of 6 patients treated at dose level 2 develops a DLT and 1 or fewer of the 6 patients treated at dose level 3 develops a DLT, then an additional 4 patients will be onto dose level 3 so that a total of 10 patients will have provided biospecimens at the MTD. (Note: Total sample size will be 6 [from dose level 1] + 6 [from dose level 2] + 6 [maximum number anticipated on dose level 3 to establish it as MTD] + 4 [for dose expansion] = 22. Biospecimens will be available for 10 patients treated at the MTD.)
- If at most 1 of 6 patients treated at dose level 3 develops a DLT then an additional 4 patients will be enrolled onto dose level 3 so that a total of 10 patients will have provided biospecimens at the MTD. (Note: Total sample size will be 6 [from dose level 1] + 3

[from dose level 2] + 6 [maximum number anticipated on dose level 3] + 4 [for dose expansion] = 19. Biospecimens will be available for 10 patients treated at the MTD.)

- If 2 or more of the 3-6 patients treated at dose level 3 develops a DLT then an additional 7 patients will be enrolled onto dose level 2 so that a total of 10 patients will have provided biospecimens at the MTD. (Note: Total sample size will be 6 [from dose level 1] + 3 [from dose level 2] + 6 [maximum number anticipated on dose level 3] + 7 [for dose expansion] = 22. Biospecimens will be available for 10 patients treated at the MTD.)

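### Four of the six enrolment branches cannot supply the 40 immunome samples planned from the expansion phase, and one branch gives 7, not 10, patients with specimens at the MTD

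*Combined protocol and SAP*

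**What the plan says.** Section 13.2 restricts the assay: "The immunome correlative will be completed in the expansion phase only". It sets four time points, "Peripheral blood will be collected at pre-treatment, after cycles 1, 3, and 6, and the PBMC fraction will be used" to quantify immune subsets, and gives the target: "We are planning to collect at least 40 longitudinal samples for the analysis". Section 12.2 has the same four draws ("Peripheral blood will be collected at pretreatment and after cycles 1, 3, and 6 for immunome studies"), as do section 9.1.4 and Table 15. The synopsis has five: "Peripheral blood will be collected at pre-treatment, after cycles 1, 3, 6 and 12 for immunome correlative studies".

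The expansion size is stated in two ways. Section 1.2 and the opening paragraph of 14.1 give a fixed 10 patients. The synopsis gives a range ("Once the MTD has been established or determined, 4-10 additional patients will be treated at the MTD of lenalidomide and ibrutinib"), and the branch rules in 7.3 and 14.1 give 10, 7 or 4 depending on the escalation result.

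Section 14.1 also says when specimen collection starts. If none of the first three patients at dose level 2 has a DLT, "biospecimen collection will begin for all subsequent patients enrolled". If one of the three does, collection starts with the second cohort of three at that level. All six branch notes then state that 10 patients at the MTD will have specimens. The last bullet enrols 7 more at dose level 2 "so that a total of 10 patients will have provided biospecimens at the MTD".

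**The concern.** The 40 is worded as a minimum, but the sections do not describe one consistent set of patients. If only expansion patients count, most branches are too small. If escalation patients at the MTD count, as the 14.1 totals imply, the restriction in 13.2 is out of step with those totals. In the last branch the 10 appears not to follow from 14.1's own rule for when collection begins.

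At stake is the stated size of the correlative objective. Anyone budgeting assays or judging what the immune profiling can show would rely on a number that the design usually cannot deliver.

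**Working it through.** **Reproducing the plan's figure.** Samples = patients × draws. With 10 patients and four draws, 10 × 4 = 40. The stated 40 therefore matches the fixed 10-patient expansion with every draw obtained.

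**Ceilings by branch.** Expansion sizes come from 14.1. Draws are four (9.1.4, 12.2, 13.2, Table 15) or five (synopsis). MTD patients with specimens = escalation patients at the MTD enrolled after collection starts + expansion patients. The last two bullets do not name the level 2 result, but their notes count 3 patients there, which corresponds to 0 of 3 with a DLT.

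| Branch in 14.1 (DLTs) | Expansion | Expansion-only ceiling, 4 draws | 5 draws | MTD patients with specimens | Their ceiling, 4 draws |
|---|---|---|---|---|---|
| Level 2: 1/3, then ≥2/6; expand level 1 | 10 | 40 | 50 | 0 + 10 = 10 | 40 |
| Level 2: ≥2/3; expand level 1 | 10 | 40 | 50 | 0 + 10 = 10 | 40 |
| Level 2: ≤1/6, level 3: ≥2; expand level 2 | 7 | 28 | 35 | 3 + 7 = 10 | 40 |
| Level 2: ≤1/6, level 3: ≤1/6; expand level 3 | 4 | 16 | 20 | 6 + 4 = 10 | 40 |
| Level 2: 0/3, level 3: ≤1/6; expand level 3 | 4 | 16 | 20 | 6 + 4 = 10 | 40 |
| Level 2: 0/3, level 3: ≥2; expand level 2 | 7 | 28 | 35 | 0 + 7 = 7 | 28 |

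The four branches with expansions of 7 or 4 stay below 40 on both schedules.

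**The last branch.** With 0/3 DLTs at level 2, collection begins only for later patients, so the first three at level 2 give no specimens. The third row follows the same logic: its 10 is the second cohort of 3 plus 7, with the first three left out. The last branch reuses the 7 but has no second cohort of 3. Its own total (6 + 3 + 6 + 7 = 22) leaves no room for one. Seven patients at the MTD have specimens, giving at most 7 × 4 = 28 samples (7 × 5 = 35 with the cycle 12 draw).

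**Attrition.** Assume that time to progression is exponential with median m and that draws stop at progression. The draws after cycles 1, 3 and 6 fall at 28, 84 and 168 days, or 0.92, 2.76 and 5.53 months at 30.4 days per month. Expected samples per patient = 1 + S(0.92) + S(2.76) + S(5.53), with S(t) = 0.5^(t/m). Two values from the document set the range of m: a median time to progression of 11.1 months (Table 1) and an event-free survival of about 5 months in doubly refractory patients (1.1.1).

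- m = 11.1: 1 + 0.944 + 0.842 + 0.708 = 3.49
- m = 5: 1 + 0.880 + 0.682 + 0.465 = 3.03

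Expected totals at four draws are about 30–35 for 10 patients, 21–24 for 7 and 12–14 for 4. The chance that all ten patients remain progression-free to the end of cycle 6 is 0.708^10 ≈ 3% at m = 11.1 and 0.465^10 ≈ 0.05% at m = 5.

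**The case against.** The best reply is that the 40 is sound and one sentence is out of date. On this view the immunome set is the 10 MTD patients of 14.1, 10 × 4 = 40 follows, and only the expansion-only restriction needs to go. Much of this stands: it probably explains the figure, and it restores a ceiling of 40 in five branches. It does not rescue the last branch, and it leaves 40 as a maximum rather than a minimum at four draws.

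It is also fair that 40 is not an absolute ceiling. Under the synopsis schedule a 10-patient expansion could give 50. The smaller expansions still fall short.

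Three stronger readings are tempting and are not supported:

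- A reader might infer that 13.2 and 14.1 flatly contradict each other on collection. Section 14.1 speaks of biospecimens in general, which include marrow for other assays. Collecting from escalation patients while limiting one assay to the expansion is possible. The mismatch lies in the counts.
- A reader might infer that escalation samples already in hand would be wasted. Sections 7.3 and 14.1 report enrolment only, not specimens, and 13.1 plans a Th1/Th2 analysis of blood and marrow with no expansion limit.
- A reader might conclude that the assay should cover every patient who gives a specimen. That would add patients treated away from the MTD and change what is studied. It is a scope decision, not a correction.

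Finally, this is an exploratory objective, worded as a plan, with no test, power or decision rule tied to 40. That limits the weight of the point.

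**Conclusion.** The point holds as a counting inconsistency. As 13.2 is written, four of six branches cannot reach 40 samples on either draw schedule, with shortfalls at four draws of 12 (40 − 28) or 24 (40 − 16). In the two level 1 branches, 40 at four draws requires every patient to give every sample. Counting escalation patients at the MTD with specimens, five branches can reach exactly 40 if no draw is missed. The last 14.1 branch gives 7 patients, not 10, whichever way 13.2 is read.

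The ceilings need no assumption beyond the number of draws. The expected numbers do rest on assumptions. Neither source population matches this trial's, the exponential shape is a convenience, and stopping for toxicity is ignored, so the range is illustrative and the conclusion does not depend on it. No MTD or safety conclusion changes, and the six branch sample-size totals add up.

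**What to change.** 1. In 13.2, replace the expansion-only restriction with the MTD patients who provide specimens under 14.1, escalation plus expansion, so that it agrees with the 3 + 7 and 6 + 4 counts.
2. In 13.2, restate the planned number of samples by branch as a maximum with an expected range. At four draws this is at most 40 (about 30–35 expected) in five branches, and at most 28 (about 21–24) in the last. The assumptions behind the expected figures should be given.
3. Correct the last 14.1 bullet, both its text and its note, to 7 patients with specimens at the MTD.
4. Reconcile the fixed expansion of 10 (section 1.2 and the opening of 14.1) with the 4–10 in the synopsis and the branch sizes in 7.3 and 14.1.
5. Reconcile the synopsis's cycle 12 draw with 9.1.4, 12.2, 13.2 and Table 15.

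The cost is text changes, less favourable stated numbers, and assays on already mandated samples from up to 6 escalation patients at the MTD (at most 6 × 4 = 24 samples). The total stays at or below 40 at four draws. No patient or draw is added. If the sponsor prefers to keep the assay in the expansion only, item 1 falls away and the maxima in item 2 become 40, 28 or 16.

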13.3. Immunohistochemistry analysis (IHC) in bone marrow biopsies

Bone marrow core biopsies collected at the same time of the bone marrow aspirates (Pre-treatment and end of cycle 1) will be used to perform IHC staining to determine levels of B-cell receptor signaling and Btk activation in the bone marrow of the myeloma patients after treatment. Phosphorylated and total Btk, phosphorylated and total PLC γ and phosphorylated and total ERK will be assessed by IHC and coexpression with CD-138+ MM cells will be also assessed. Furthermore, by RT-PCR we will evaluate the variation in BTK mRNA levels associated to the treatment as previously described.

13.4. Measurement of Effect

Patients enrolled onto this trial must have measurable disease defined as disease that can be measured either by serum or urinary evaluation of the monoclonal component or by serum assay of FLC and is defined by at least one of the following three measurements:

- Serum M-protein > (0.5 g/dl) g/dl
- Urine M-protein > 200 mg/24 h
- Serum FLC assay: Involved FLC level > 10 mg/dl (> 100 mg/l) provided serum FLC ratio is abnormal.

The disease response will be assessed using criteria based on the International Working Group Uniform Response Criteria in Section 15.3.1. If the only measurable parameter is serum immunoglobulins free light chain (FLC), the participant will be followed by FreeLite™ Disease Response Criteria provided in Section 15.3.2.

The same method of assessment and technique should be used for disease measurement

throughout the study. Disease response should be confirmed by two consecutive assessments at a minimum of 6 weeks apart.

13.5. Methods for Evaluation of Measurable Disease

All baseline evaluations should be performed on Cycle 1, Day 1 of therapy. Response will be assessed by M-protein quantification, protein electrophoresis and immunofixation from serum, a 24-hour urine collection and serum free light chain. In addition, bone marrow aspiration and biopsy will be performed to confirm CR and differentiate between CR and stringent CR.

13.6. Response Criteria

13.6.1 International Myeloma Working Group Response Criteria

Table 17

Response	IMWG criteria
sCR	CR as defined below plus normal FLC ratio and absence of clonal cells in bone marrow by immunohistochemistry or 2 – 4 color flow cytometry
CR	Negative immunofixation on the serum and urine and disappearance of any soft tissue plasmacytomas and < 5% plasma cells in bone marrow. In patients with only FLC disease, a normal FLC ratio of 0.26–1.65 is required.
VGPR	Serum and urine M-protein detectable by immunofixation but not on electrophoresis or ≥ 90% reduction in serum M-protein plus urine M-protein level < 100 mg/24 h In patients with only FLC disease, >90% decrease in the difference between involved and uninvolved FLC levels is required.
PR	≥ 50% reduction of serum M-protein and reduction in 24 hours urinary M-protein by ≥90% or to < 200 mg/24 h If the serum and urine M-protein are unmeasurable, a ≥ 50% decrease in the difference between involved and uninvolved FLC levels is required in place of the M-protein criteria
Stable disease	Not meeting criteria for CR, VGPR, PR, or progressive disease

Progressive disease	
Increase of $\geq 25\%$ from lowest response value in any one or more of the following:
 
Serum M-component and/or (the absolute increase must be $\geq 0.5 \text{ g/dL}$) Urine M-component and/or (the absolute increase must be $\geq 200 \text{ mg/24 h}$) Only in patients without measurable serum and urine M-protein levels; the difference between involved and uninvolved FLC levels. The absolute increase must be $> 10 \text{ mg/dL}$
 
Definite development of new bone lesions or soft tissue plasmacytomas or definite increase in the size of existing bone lesions or soft tissue plasmacytomas Development of hypercalcaemia (corrected serum calcium $> 11.5 \text{ mg/dL}$ or 2.65 mmol/L) that can be attributed solely to the plasma cell proliferative disorder

---------------------	--

Additional response criteria for specific disease states

Minor response in patients with relapsed and refractory myeloma adapted from the EMBT Criteria $\geq 25\%$ but $< 49\%$ reduction of serum M protein and reduction in 24-hour urine M protein by 50 – 89%, which still exceeds 200 mg/24hrs. In addition to above; if present at baseline, 25-49% reduction in the size of soft tissue plasmacytomas is also required. No increase in size or number of lytic bone lesions (development of compression fractures does not exclude response).

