14.3.2 Statement for Primary Endpoint

The primary endpoint of the dose escalation portion of this phase I study is the MTD. The maximum tolerated dose is defined as the highest dose level among those tested where at most one out of 6 patients develops a DLT prior to the start of their second cycle of treatment and the next highest dose level is such that 2 or more patients among the maximum of 6 patients treated at that dose level developed a DLT prior to the start of their second cycle of treatment.

The primary endpoint of the expansion portion of this phase I study is the objective response rate. The objective response rate is the percent of patients who meet the International Myeloma Working Group Response Criteria for sCR, CR, VGPR, or PR on two consecutive evaluations at least 4 weeks apart among the patients who began study treatment. A 90% binomial confidence interval will be constructed for the overall objective response rate.

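### PR and VGPR carry no soft tissue plasmacytoma condition although CR and minor response do, so a patient with a persistent lesion can count as a responder and ORR can be overstated

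*Combined protocol and SAP*

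**What the plan says.** Section 13.6.1 of the protocol treats soft tissue plasmacytomas as follows.

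- **CR (Table 17):** "Negative immunofixation on the serum and urine and disappearance of any soft tissue plasmacytomas", together with a marrow condition. sCR builds on CR and so inherits this.
- **VGPR (Table 17):** "Serum and urine M-protein detectable by immunofixation but not on electrophoresis or" a 90% fall in serum M-protein with low urine M-protein, or an FLC equivalent. Plasmacytomas are not mentioned.
- **PR (Table 17):** at least a 50% "reduction of serum M-protein and reduction in 24 hours urinary M-protein by" at least 90% or to below 200 mg/24 h, or an FLC equivalent. Plasmacytomas are not mentioned.
- **Minor response (paragraph after Table 17):** "if present at baseline, 25-49% reduction in the size of soft tissue plasmacytomas is also required".
- **Progressive disease (Table 17):** includes new plasmacytomas or a "definite increase in the size of existing bone lesions or soft tissue plasmacytomas".
- **Stable disease (Table 17):** whatever is not CR, VGPR, PR or progression.

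In Section 13.6.2, Table 18, which serves patients measurable only by FLC, the PR row rests on FLC changes alone.

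Section 14.3.2 makes the objective response rate the primary endpoint of the expansion. It counts sCR, CR, VGPR or "PR on two consecutive evaluations at least 4 weeks apart among the patients who began study treatment", and attaches a 90% binomial interval.

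**The concern.** The plasmacytoma requirement appears at the top of the scale and again in a category below PR, but not in the two categories between them. PR and VGPR are where the line between responder and non-responder is drawn. Read literally, the table lets a patient with a visible lesion that has not responded count as a success on serum, urine or FLC results alone.

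Assessors may also differ. Some will apply the rows as printed and others will infer a lesion requirement from the neighbouring rows. In a cohort of about 10 patients, one such call changes the reported ORR visibly.

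**Working it through.** **1. Is the gap filled elsewhere?** Section 13.5 lists the response methods as serum, urine and FLC tests, with marrow to confirm CR; imaging is not among them. Section 14.3.2 adds only the confirmation rule. No other section supplies a lesion condition for PR or VGPR. (The CR row of Table 18 is also silent, but the CR row of Table 17 has its own FLC-only sentence and does carry the condition.)

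**2. Are the categories nested?** Take two patients with the same unchanged baseline plasmacytoma.

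- *Patient A:* serum M-protein falls 30% and urine M-protein falls within the minor-response band. The unchanged lesion disqualifies A from minor response.
- *Patient B:* serum M-protein falls 60% and the urine PR condition is met. The lesion is not considered. B is PR and, if confirmed, a responder.

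The progression row does not catch B, because the lesion has not grown. The stable-disease row does not either, because B meets PR. The same lesion counts against the lesser response and is ignored for the greater one.

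**3. Can such patients be on study?** Eligibility rests on M-protein or FLC, and no exclusion criterion removes patients with soft tissue plasmacytomas. Section 9.1.1 and Table 15, footnote e, provide for a repeat scan in patients with extramedullary disease on the baseline scan. They are foreseen, but no number is given.

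**4. Direction.** Adding a condition to PR and VGPR can only remove responders or leave the count unchanged. Any error in ORR from this gap is therefore upward.

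**5. Size per affected patient.** The plan states no expected ORR, null rate or interval width, so there is no figure to reproduce. Response counts below are illustrative. The shift per patient is 1/n; the exact 90% limits are the 5th percentile of Beta(x, n−x+1) and the 95th percentile of Beta(x+1, n−x).

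| n | As written | One patient reclassified | Shift |
|---|---|---|---|
| 10 | 5/10 = 50% (22.2-77.8%) | 4/10 = 40% (15.0-69.6%) | 10 points |
| 19 | 11/19 = 57.9% (36.8-77.0%) | 10/19 = 52.6% (32.0-72.6%) | 5.3 points |
| 25 | 15/25 = 60% (41.7-76.4%) | 14/25 = 56% (37.9-73.0%) | 4 points |

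Here 10 is the expansion size in Section 14.1, and 19 and 25 are the limits of total enrolment in the synopsis and Section 3.

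**6. Chance that it matters at all.** Let q be the share of treated patients with a persistent baseline plasmacytoma and a biochemical PR or VGPR. The documents do not give q; 1% to 10% is an assumed range. P(at least one) = 1 − (1 − q)^n.

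| q | n = 10 | n = 25 |
|---|---|---|
| 1% | 9.6% | 22.2% |
| 2% | 18.3% | 39.7% |
| 5% | 40.1% | 72.3% |
| 10% | 65.1% | 92.8% |

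The expected overstatement of ORR equals q, that is 1 to 10 points over this range.

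**The case against.** The best case on the other side has four parts.

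*The number affected is unknown and may be zero.* This stands. A reader might infer that ORR **is** overstated; the documents support only that it **can be**. The exposed group is also narrower than all patients with plasmacytomas, because Table 17 already makes definite growth or a new lesion progression.

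*Minor response is a weak comparator.* It is adapted from a different set of criteria, is presented as an addition to the table, and does not count towards ORR. That is fair, but the CR row of Table 17 itself carries a plasmacytoma condition, and the gap in PR and VGPR exists without the comparison.

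*No decision hangs on ORR.* There is no target or go/no-go rule, and Sections 2.2 and 2.4.1 list ORR as secondary. This limits the consequence. Section 14.3.2 nevertheless calls ORR the primary endpoint of the expansion, and an estimate with its interval is all that endpoint delivers.

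*The imaging is too sparse to support a lesion rule.* Follow-up CT is done only where clinically indicated, at the end of cycle 6 or to confirm CR. This stands against any rule that makes every patient without a scan a non-responder: patients who leave before cycle 6, or whose scan was not indicated, would fail because of the schedule, and a downward bias would replace the upward one. It does not stand against using the scans that exist.

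Two further inferences are tempting and unsupported. One is a 25-point shift per patient, from reading the 4-patient expansion as the denominator. Under Section 14.1 those 4 patients join 6 already treated at dose level 3, and Section 14.3.2 refers to patients who began treatment. The other is that duration of response is biased upward. Nothing in the documents implies this; adding patients with residual lesions could equally shorten it.

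**Conclusion.** The gap is real on the text alone. As written, PR and VGPR in Table 17 and PR in Table 18 admit patients whose baseline plasmacytoma is unchanged or insufficiently reduced, and those patients count in the expansion's primary endpoint. Its effect on ORR can only be upward or nil: 10 points per affected patient with 10 patients, and 4 to 5 points with 25 to 19. How many patients are affected is not given, so the total effect rests on the assumed share above. The point should be settled before analysis; it does not show that any reported ORR will be wrong.

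**What to change.** 1. Add to the PR and VGPR rows of Table 17 and the PR row of Table 18: *if a soft tissue plasmacytoma was present at baseline, its size must also have fallen by at least 50%*. This is the band left open between minor response (up to 49%) and CR (disappearance). It is inferred from the table's own structure; if the sponsor prefers another threshold, it should state and justify it.
2. Add to Section 14.3.2 that the condition is judged on the lesion assessments already provided for in Section 9.1.1 and Table 15, footnote e. A patient whose available follow-up assessment does not meet it is not a responder.
3. Do not automatically count patients with a baseline plasmacytoma and no follow-up scan as non-responders. Flag them and report their number. Show ORR with them counted as non-responders, and ORR on M-protein/FLC alone.

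The cost is one line in each of three table rows and a short addition to Section 14.3.2, with no new procedure. ORR may come out slightly less favourable. Because repeat CT is done only where clinically indicated, some patients will have no follow-up scan, and the two ORR figures will show how much that matters.
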